2.1.3 Pharmacokinetic analysis set

The Pharmacokinetic (PK) Analysis Set (PKS) will consist of all patients participating in the subset of the PK patients, who received at least 1 dose of AZD8871 and have at least 1 of the

parameters C_{max} , $AUC_{(0-24)}$ or AUC_{last} evaluable for AZD8871 and are assumed not to be affected by factors such as protocol deviations (e.g., prohibited concomitant medications which are thought to impact on the PK data, or incorrect study medication received).

All protocol deviations that occur during the study will be considered for their severity/impact and will be taken into consideration when patients are assigned to the PK analysis sets. The exclusion of any patients or time-points from the calculation of the PK parameters and/or from the PK summary statistics will be agreed at the blinded data review meeting and it will be documented by the PK Scientist including the reason(s) for exclusion. The available concentration data and PK parameter data for any patients excluded from the PK analysis set for a given study period will be listed only. Concentration data for patients excluded from the PK analysis set will be presented in the individual figures of concentration versus time plots.

2.1.4 Per-Protocol Analysis Set

The Per-Protocol Analysis Set (P-PS) is defined as a subset of FAS population constituted by those patients who did not present important deviations of the protocol that may affect efficacy (eg, met all inclusion/exclusion criteria liable to affect the efficacy assessment).

2.2 Violations and deviations

Only important protocol deviations that may greatly impact the completeness, accuracy, and/or reliability of the study data or that may significantly affect a patient's rights, efficacy, safety, or well-being will be summarised and listed.

Important protocol deviations include:

- Key eligibility criteria not fulfilled but patient randomised
- Disallowed concomitant medication taken during the study
- Developed discontinuation criteria but not withdrawn from study or discontinued investigational product, as appropriate
- Received incorrect study drug

A sensitivity analysis based on the P-PS will be conducted for internal validity purposes, whereby patients with important deviations from protocol deemed to affect efficacy will be excluded from the analysis.

Table 1 shows the protocol deviations which will lead to exclusion from P-PS, PKS, SS, or FAS. During the blind data review (BDR) the final list of the important protocol deviations affecting efficacy will be finalized and documented prior to unblinding of the study data.

Table 1 Major protocol deviations and population classification

Item #	Event description	Excluded from analysis set			
		P-PS	SS	PKS	FAS
1.	Provision of informed consent not performed before any study specific procedures.	Yes	No	No	No
2.	ICF source document not available at site, or any issue with the ICF document.	Yes	No	No	No
3.	Subject must be able to read, speak and understand local language.	Yes	No	No	No
4.	Female Patient has childbearing potential	Yes	No	No	No
5.	Male patient did not prevent pregnancy and drug exposure of a partner.	Yes	No	No	No
6.	Patient has alpha-1 antitrypsin deficiency as the cause of COPD (laboratory results will be used in combination with smoking and medical history).	Yes	No	No	No
7.	Patient is less than 40 or more than 85 years of age	Yes	No	No	No
8.	Patient has no established clinical history of moderate to severe COPD for more than 1 year at Screening	Yes	No	No	No
9.	Patient is not current or former smoker with a history of ≥ 10 pack-years of cigarette smoking and/or not smoking other types of tobacco (including e-cigarettes).	Yes	No	No	No
10.	Patient has post-bronchodilator FEV ₁ /FVC ratio is $\geq 70\%$ based on the value reached after inhalation of salbutamol (400 µg) at Visit 2	Yes	No	No	No
11.	Patient with post-bronchodilator FEV ₁ $< 40\%$ or $\geq 80\%$ predicted normal value at Visit 2.	Yes	No	No	No
12.	Patient with body mass index (BMI) ≥ 40 kg/m ² at the time of Screening	Yes	No	No	No
13.	Patient has a clinically significant disease, other than COPD, that may impact study outcome, as determined by medical history, physical examination, laboratory testing, and 12-lead ECG findings, at Screening.	Yes	No	No	No
14.	Patient has other active pulmonary disease such as predominant asthma, active tuberculosis, lung cancer, bronchiectasis, sarcoidosis, idiopathic interstitial pulmonary fibrosis, primary pulmonary hypertension, or uncontrolled sleep apnoea.	Yes	No	No	No
15.	Patient has undergone lung volume reduction surgery, lung transplantation, lobectomy, or bronchoscopic lung volume reduction within 1 year of Screening.	Yes	No	No	No
16.	Patient is using nocturnal positive pressure	Yes	No	No	No
17.	Patient has been hospitalised due to poorly controlled COPD within 3 months of Screening.	Yes	No	No	No
18.	Patient has acute worsening of COPD that required antibiotics or corticosteroids in the 6-week interval prior to Screening (Visit 1), or during the Screening Period (between Visits 1 and 2).	Yes	No	No	No
19.	Patient has lower respiratory tract infections that required antibiotics within 6 weeks prior to Screening.	Yes	No	No	No
20.	Patient has changed their smoking status (ie, restart or stop smoking) or initiation of a smoking cessation program within 6 weeks of Screening.	Yes	No	No	No
21.	Subject with significant cardiovascular disease that may be vulnerable to cardiovascular instability.	Yes	No	No	No
22.	Patient with QT interval corrected using Fridericia's formula (QTcF) value at Screening > 450 ms for male and > 470 ms for female or an ECG that is not suitable for QT measurements (eg, poorly defined termination of the T wave).	Yes	No	No	No
23.	Patient with heart rate < 50 or > 100 bpm at Screening.	Yes	No	No	No
24.	Patient has clinically significant uncontrolled hypertension as assessed by the investigator.	Yes	No	No	No
25.	Patient with seizures or history of seizures requiring anticonvulsants within 12 months prior to Screening.	Yes	No	No	No
26.	Patient is taking selective serotonin reuptake inhibitors or serotonin-norepinephrine reuptake inhibitors whose dose has not been stable for at least 4 weeks prior to Screening, or exceeds the maximum recommended dose.	Yes	No	No	No

Item #	Event description	Excluded from analysis set			
		P-PS	SS	PKS	FAS
27	Patient with symptomatic bladder neck obstruction, acute urinary retention or symptomatic non-stable prostate hypertrophy.	Yes	No	No	No
28	Patient has a serum potassium value <3.5 mmol/L at Screening and on repeat testing, uncontrolled diabetes and any clinically relevant lab abnormality. Note: however potassium replacement and rescreening is allowed once if serum potassium concentration was <3.5 mmol/L at Screening.	Yes	No	No	No
29	History of malignancy of any organ system, treated or untreated within the past 5 years, with the exception of localised basal cell carcinoma of the skin.	Yes	No	No	No
30	Patient has known narrow-angle glaucoma.	Yes	No	No	No
31	Patient has a history of hypersensitivity to β_2 -agonists, muscarinic anticholinergics or lactose/milk protein. Lactose intolerance is not an exclusion criterion.	Yes	No	No	No
32	The patient has a history of drug of abuse within the past 2 years or consuming more than 14 (female patients) or 21 (male patients) units of alcohol a week, or shows positive for drugs of abuse and alcohol tests at Screening and/or prior to randomisation.	Yes	No	No	No
33	Patient received a live attenuated vaccination within 30 days prior to Screening.	Yes	No	No	No
34	Patient donated or lost >500 mL of blood and plasma within the previous 3 months prior to Screening	Yes	No	No	No
35	Vulnerable patients (who has been placed in an institution due to a regulatory or court order)	Yes	No	No	No
36	Patient is unlikely to co-operate with the requirements of the study, instructions of the Principal Investigator (PI), or have e-dairy completion rate of <70% during the run-in period.	Yes	No	No	No
37	Involvement in the planning and/or conduct of the study (applies to both AstraZeneca staff and/or staff at the study site).	Yes	No	No	No
38	Patient previously enrolled in the present study	Yes	Yes	Yes	Yes
39	Patient has participate in the acute phase of a pulmonary rehabilitation program within 4 weeks prior to Screening or who will enter the acute phase of a pulmonary rehabilitation program during the study.	Yes	No	Yes	Yes
40	Patient non-compliance with study procedures, unable to change current COPD therapy as required by the protocol and not willing to use ipratropium following the approved dosage and regimen – as judged by the investigator.	Yes	No	Yes	Yes
41	Patient is unwilling to remain at the study centre as required per protocol to complete all visit assessments.	Yes ⁺⁺⁺	No	Yes ⁺⁺⁺	No
42	Participation in another clinical study with investigational drug or device within the last 30 days or 5 half-lives (whichever is longer) prior to Screening.	Yes ⁺⁺⁺	No	Yes ⁺⁺⁺	No
43	Patient with known human immunodeficiency virus (HIV) infection or chronic hepatitis B or C infection.	Yes	No	No	No
44	Patient did not fulfill fasting requirements on Day 1, 8, and 14 before IP administration and following dose administration.	Yes ⁺⁺	No	No	No
45	Salbutamol not withheld at least 6 hours prior to any spirometry test for the study.	Yes	No	No	No
46	Ipratropium not withheld at least 8 hours before visits 3, 6, and 9 and during all treatment periods.	Yes	No	No	No
47	Patient could not abstain from list in protocol section 5.3	Yes	No	No	No
48	Patient who had 2 or more exacerbations of COPD within the last year prior to Screening	Yes	No	No	No
49	Patient unable to abstain from protocol-defined prohibited medications during the study, in the opinion of the investigator.	Yes ⁺⁺	No	Yes ⁺⁺	No
50	Patient is screening failure, but received study drug.	Yes	Yes	Yes	Yes
51	Incorrect study medication received.	Yes ⁺⁺	No	Yes ⁺⁺	No

Item #	Event description	Excluded from analysis set			
		P-PS	SS	PKS	FAS
52	Incorrect dose of study medication received.	Yes ⁺⁺	No	Yes ⁺⁺	No
53	Patient did not take any IP	Yes ⁺⁺	Yes	Yes ⁺⁺	Yes ⁺⁺
54	IP not taken at the study site at 9:00 AM±2 hours on Day 1 (Visits 3, 6 and 9).	Yes ⁺⁺	No	Yes ⁺⁺⁺	No
55	IP not taken within ±1 hours of dosing time of Day 1 and between 7 AM and 11AM on subsequent days of each treatment period.	Yes ⁺⁺	No	Yes ⁺⁺⁺	No
56	Patient has taken any of the restricted medications on a different regimen than the described in the protocol (Table 5, section 6.5).	Yes ⁺⁺	No	Yes ⁺⁺⁺	No
57	Procedure not performed (missing PK samples to prevent calculation of PK parameters).	No	No	Yes ⁺⁺	No
58	Study assessments (For example cough monitoring, spirometry, CC1 i-Stat, 12 Lead ECG and/or vital signs) are not performed at the scheduled timepoints.	No	No	No	No
59	Missing baseline data for the spirometry (FEV1 main variable)	Yes ⁺⁺	No	No	No
60	FEV1 and FVC measurements performed outside tolerance window	No	No	No	No
61	Fulfilling withdrawal criteria during the study but not withdrawn.	Yes	No	No	No
62	Fatal or life-threatening AE was not reported to the appropriate AstraZeneca representatives within 1 calendar day of initial receipt.	No	No	No	No
63	Non-fatal, and non-life-threatening SAE was not reported to the appropriate AstraZeneca representatives within 5 calendar days of initial receipt.	No	No	No	No
64	Date of Screening Visit 1 is after date of Screening Visit 2.	No	No	No	No
65	Visit date is after the Completed date.	No	No	No	No
66	Any of the study visits not performed within the allowed time as per protocol.	No	No	No	No
67	Other protocol deviations	Yes ⁺⁺⁺	No	Yes ⁺⁺⁺	No

⁺⁺Excluded from the specific timepoint or period only. ⁺⁺⁺ To be confirmed at the DRM; timepoint specific, global P-PS/PKS exclusion or no exclusion.

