2. ANALYSIS SETS

2.1 Definition of analysis sets

2.1.1 Full analysis set

The Full Analysis Set (FAS) is defined as all patients randomised and receiving IP, irrespective of their protocol adherence and continued participation in the study. Patients will be assigned according to their randomised treatment, irrespective of whether or not they have prematurely discontinued. Patients who withdraw consent to participate in the study are included up to the date of their study termination. All efficacy analyses are based on the FAS and analysed according to the intent to treat principle.

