2.1.2 Safety analysis set

The Safety Analysis Set (SS) consists of all randomised patients who receive at least one dose of IP. For summaries based on the SS, patients are included for a treatment only if they received at least one dose of that treatment (e.g. a patient who discontinues prior to taking the study treatment for period 2 will not be included in the safety set for that treatment).

The SS will be used for all summaries of safety data, and patients will be analysed according to the randomised treatment assignment for a given study period. Any important deviations from the randomised treatment assignment and any patients who received IP without being randomised for a given study period will be listed and considered when interpreting the safety data. Relevant safety summaries presented by actual treatment received will be considered if there are a considerable number of patients receiving another treatment than the one they were randomised to.

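### SAP Table 1 removes dosed patients from the full analysis set (items 38–40) and the safety set (item 38), against both sets' own definitions

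*SAP*

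**What the plan says.** SAP 2.1.1 defines the FAS as "all patients randomised and receiving IP, irrespective of their protocol adherence and continued participation in the study", and adds that all efficacy analyses use it on the intent-to-treat principle. SAP 2.1.2 says the safety set "consists of all randomised patients who receive at least one dose of IP". Protocol 9.3 gives both definitions in the same sense. Neither document makes membership of either set depend on deviations.

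SAP 2.2 then introduces a table of deviations: "Table 1 shows the protocol deviations which will lead to exclusion from P-PS, PKS, SS, or FAS". Three of its rows exclude from the FAS:

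- Item 38: "Patient previously enrolled in the present study". Excluded from all four sets.
- Item 39: "Patient has participate in the acute phase of a pulmonary rehabilitation program within 4 weeks prior to Screening", or entering such a programme during the study. Excluded from the per-protocol, PK and full analysis sets, but kept in the safety set.
- Item 40: "Patient non-compliance with study procedures, unable to change current COPD therapy as required by the protocol and not willing to use ipratropium", as judged by the investigator. Same pattern as item 39.

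None of these cells carries the ++ mark (exclusion limited to a timepoint or period) or the +++ mark (to be settled at the data review meeting).

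**The concern.** A patient who is randomised, takes study drug and falls under item 38, 39 or 40 belongs to the FAS by definition and is out of it by Table 1. Under item 38 the same holds for the safety set. The FAS carries the primary analysis (SAP 4.2.2) and, through the change declared in SAP section 6, the demographic and baseline tables. The safety set carries all safety summaries (SAP 4.4).

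Following Table 1, the primary set would no longer be the intent-to-treat set the plan describes, and an exposed patient could disappear from the safety tables. Following 2.1.1 and 2.1.2, neither would happen. The plan does not say which text prevails.

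**Working it through.** The plan attaches no figure to this point, so the check compares the passages and counts the rows of Table 1.

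**1. Reading the columns.** The order is per-protocol, safety, PK, FAS. Item 57 (missing PK samples) has its only Yes in the third column, which confirms that PK is third and FAS fourth.

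**2. The rows against the definitions**, for a patient who was randomised and dosed:

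| Item | Safety set by 2.1.2 | Safety set by Table 1 | FAS by 2.1.1 | FAS by Table 1 |
|---|---|---|---|---|
| 38 | in | **out** | in | **out** |
| 39 | in | in | in | **out** |
| 40 | in | in | in | **out** |

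Four cells conflict: three for the FAS and one for the safety set.

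**3. Can such a patient exist?** The plan expects it. SAP 2.2 lists among important deviations "Key eligibility criteria not fulfilled but patient randomised", and protocol 7.3 covers patients randomised or started on treatment in error. Item 38 corresponds to exclusion criterion 26, item 39 to exclusion 29, and item 40 to inclusion 7 with an element of exclusion 30. Items 39 and 40 can also arise after randomisation, through rehabilitation begun during the study or through non-compliance.

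**4. Consistency within the table (67 rows).**

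- FAS = Yes: items 38, 39, 40, 50 and 53, so 5 rows. Item 50 (screening failure given drug) and item 53 (no drug taken) concern patients not randomised or not dosed. They fit the definitions and are not in question.
- Safety set = Yes: items 38, 50 and 53, so 3 rows.
- Safety set = No with FAS = Yes: items 39 and 40 only. At patient level the two sets have the same entry conditions (randomised, and drug taken), so the definitions cannot produce this pattern.
- Rows about consent or eligibility: items 1–43, 48 and 49, so 43 + 2 = 45. FAS = Yes in 3 (3/45 = 6.7%) and FAS = No in 42. Safety set = Yes in 1 (item 38).
- Close neighbours go the other way. Item 36 (unlikely to co-operate) and items 46, 51, 52 and 61 (ipratropium not withheld, wrong drug, wrong dose, withdrawal criteria met but not withdrawn) all have FAS = No.

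**5. Is a change declared?** SAP section 6 lists one analysis-set change, the use of the FAS for demographics. It lists no change to either definition.

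**6. Scale.** One excluded patient is 1/72 = 1.4% of the planned number. For context on power, the stated 90% reproduces. With a 100 mL difference, SD of differences 220 mL and 54 evaluable patients, the noncentrality is 100/(220/√54) = 3.34, and a two-sided 5% paired t test has power 0.906. If, as an assumption, 1, 2, 3 or 5 of the 54 were removed, power would be 0.901, 0.895, 0.889 or 0.877. Power is not the issue.

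**The case against.** The strongest reply is that the protocol delegates the matter. Section 9.4 allows important deviations to exclude patients from populations other than the per-protocol set, names eligibility violations among such deviations, and leaves the precise reasons to the SAP. On that reading rows 38–40 are a permitted specific rule. But the same section requires patients to be assigned according to the specified definitions, and the SAP repeats those definitions without qualification. Delegation makes this a drafting conflict inside the SAP; it does not resolve it.

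Protocol 7.3 also says an ineligible patient who was started on treatment must stop and be excluded from the study. That most naturally concerns participation, and the FAS applies regardless of continued participation.

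The blind data review might catch the conflict. However, the discretion that Table 1 gives that meeting (+++) is attached only to per-protocol and PK cells.

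Some of the reply stands. Populations are fixed blind and a whole patient is removed in a crossover, which limits treatment-related bias. All reported adverse events are still listed (SAP 4.4.1.1), so item 38 affects safety tables rather than reporting. Eligibility is screened and waivers are barred, so few patients, perhaps none, will be affected. The count of 45 rows involves some classification: without item 2 (consent source document) it is 3/44 = 6.8%. For item 38, a wish to avoid counting one person twice would be reasonable, but the SAP does not state it.

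**Conclusion.** The concern holds. Four cells of SAP Table 1 (FAS for items 38, 39 and 40; safety set for item 38) contradict the definitions in SAP 2.1.1, SAP 2.1.2 and protocol 9.3, and no declared change covers them. The practical size is unknown and may be nil, and no bias or material loss of power is asserted. The conclusion assumes Table 1 is applied as written to a patient who was randomised and dosed. It merits correction because the sets for the primary analysis and for safety should each have one rule, settled before unblinding.

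**What to change.** Before database lock:

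1. Set FAS = No for items 38, 39 and 40, and safety set = No for item 38.
2. Leave their per-protocol and PK exclusions alone. SAP 2.1.4 already removes deviations that may affect efficacy, and SAP 2.1.3 admits to the PK set only patients who "are assumed not to be affected by factors such as protocol deviations".
3. If the sponsor wants to keep the FAS or safety-set exclusions, amend the definitions in SAP 2.1.1 and 2.1.2 and declare the departure from protocol 9.3 in SAP section 6, with the reason.
4. For item 38, align the wording with exclusion criterion 26. Protocol section 5 defines enrolment as signing consent and 5.4 permits limited rescreening, so state that permitted rescreening is not caught. If double counting is the worry, add a count-once rule; which participation counts is the sponsor's choice.
5. Optionally, make clear that item 50 refers to patients who were not randomised.

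The cost is four table cells and, for item 38, a line or two of text. No patients, data collection, or per-protocol or PK rules change.

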4.2 Scientific rationale for study design

The objective of the study is to assess the efficacy, safety and pharmacokinetics (PK) of AZD8871 600 μ g after a 14-day treatment period in patients with moderate to severe COPD. The target population includes male and female (non-childbearing potential) adult patients with clinical diagnosis of moderate to severe COPD as per the criteria of the GOLD guidelines.

A double-blinded, double-dummy design has been chosen to limit the occurrence of conscious and unconscious bias in the conduct and interpretation of a clinical study arising from the influence which the knowledge of treatment may have on the recruitment and allocation of patients. It is considered the optimal approach according to International Conference on Harmonisation (ICH) E9 “Statistical principles in clinical studies.”

The crossover design has been chosen to avoid inter-patient variability and optimize sample size. Based on the information of terminal elimination half-lives observed for AZD8871 and LAS191861 from previous clinical studies, the wash-out period proposed for this current study is a minimum of 42 days and up to 49 days in order to avoid any carry-over effect between periods.

By randomly assigning treatment sequence, differences in baseline characteristics of the treatment groups will be minimised. The inclusion of a placebo arm is considered the most reliable method to minimise patient and Investigator bias according to ICH Topic E10 (Choice of control group in clinical trials) ICH/364/96 guideline adopted by the Committee for Proprietary Medicinal Products (CPMP), CPMP/EWP/562/98 and Food and Drug Administration (FDA).

AZD8871 will be evaluated by directly comparing it against Anoro[®] Ellipta[®]; the best-in-class once daily LAMA and LABA fixed-dose combination ([Feldman et al, 2017](#)).

Since COPD patients present with multiple comorbidities, a placebo arm has been added to better characterise the safety profile of the product. The inclusion of a placebo treatment will enhance the interpretation of the difference in safety and efficacy outcomes between active arms. This is due to the limited available data for Anoro[®] Ellipta[®] in this specific COPD patient population and the endpoints that will be assessed.

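### The per-protocol set keeps periods begun after a short wash-out and baseline or trough readings outside their window, while the exclusion unit for a single mistimed dose is left undefined

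*SAP*

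**What the plan says.** SAP 2.1.4 limits the per-protocol set to patients "who did not present important deviations of the protocol that may affect efficacy". SAP 2.2 uses that set for a sensitivity analysis, and SAP 4.2.2 applies it to the primary variable. The secondary FEV1 analyses in SAP 4.2.3 and 4.2.4 use the full analysis set only.

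The rows of SAP Table 1 that matter here are:

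- Item 66, "Any of the study visits not performed within the allowed time as per protocol": No for all four sets.
- Item 60, "FEV1 and FVC measurements performed outside tolerance window": No for all four sets.
- Item 58, study assessments (spirometry is named) that "are not performed at the scheduled timepoints": No for all four sets.
- Item 55, "IP not taken within ±1 hours of dosing time of Day 1 and between 7 AM and 11AM on subsequent days": Yes++ for the per-protocol set, with no minimum number of doses.

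The ++ footnote confines an exclusion to either a time point or a period, and does not say which applies to which row.

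Protocol Table 1, footnote d, sets 42 to 49 days from the last dose between treatment periods. Protocol 4.2 gives the reason: "a minimum of 42 days and up to 49 days in order to avoid any carry-over effect between periods". Trough FEV1 is defined as the mean of the 23 h and 23 h 45 min readings (Protocol 9.4.1, SAP 3.3.1).

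**The concern.** In a three-period crossover with a trough endpoint, two protocol deviations bear directly on the primary contrast: starting a period before the previous treatment has washed out, and reading FEV1 at times other than those that define baseline or trough. A per-protocol analysis would be expected to remove both. As coded, it removes neither, and no limit is placed on how short the wash-out or how mistimed the reading may be.

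A dose more than an hour off schedule does trigger exclusion, although most such doses would be home doses taken before the supervised Day 14 dose that precedes the trough. If the per-protocol and full-set results agree, the agreement will say nothing about short wash-outs or mistimed readings, because both analyses contain them.

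**Working it through.** **1. The plan's own figure.** Protocol 9.2 gives a target difference of 100 mL, SD of differences 220 mL, two-sided 5%, 90% power and 54 evaluable patients. With a paired t-test (noncentral t) the smallest n reaching 90% is 53, and power at 54 is 0.906. Dropout: 54/(1 − 0.25) = 72. The figures reproduce and are not in dispute.

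**2. Where a short wash-out falls.** Footnote d is attached to Visits 3, 6 and 9. A Visit 6 or 9 held too early is thus a visit outside its allowed time. No other Table 1 row names wash-out, so item 66 governs. Periods removed from the per-protocol set for a wash-out under 42 days: 0.

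**3. Where a mistimed reading falls.** A baseline or trough reading off its time falls under item 58 or 60. Readings removed: 0. Item 59, in contrast, codes a missing FEV1 baseline as Yes++. A missing baseline can therefore be excluded, and a mistimed one is kept.

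**4. What item 55 can remove.** Protocol Table 1, footnote u: Days 1, 2, 8 and 14 are dosed at the site; Days 3–7 and 9–13 at home, so 5 + 5 = 10 home doses per period. None of those ten days has scheduled spirometry.

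- *Time-point reading:* a mistimed home dose has no FEV1 reading attached to it, so no Day 15 trough is lost.
- *Period reading:* one mistimed home dose removes that period's Day 15 trough.

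**5. Illustration of the period reading only.** Let q be the chance that a home dose is more than 1 h off. The documents give no value, so q is assumed and doses are treated as independent. A complete AZD8871–Anoro pair needs 2 × 10 = 20 doses on time:

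pairs kept = 54 × (1 − q)^20, rounded down

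half-width of the 95% CI = t(0.975, n − 1) × 220/√n

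| q | (1 − q)^20 | Pairs | Power | Half-width (mL) |
|---|---|---|---|---|
| 0 | 1.000 | 54 | 0.91 | 60 |
| 0.5% | 0.905 | 48 | 0.87 | 64 |
| 1% | 0.818 | 44 | 0.84 | 67 |
| 2% | 0.668 | 36 | 0.76 | 74 |
| 5% | 0.358 | 19 | 0.47 | 106 |

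On the time-point reading every row stays at 54.

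**The case against.** The strongest reply is that carry-over is handled elsewhere:

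- Pre-dose FEV1 at Visits 6 and 9 must lie within ±20% or ±200 mL of Visit 3, and repeated failure leads to withdrawal (Protocol 8.1.2). A patient who met withdrawal criteria but stayed is excluded by item 61.
- The primary model adjusts for each period's pre-dose FEV1.
- Protocol 9.4.1 promises a full-set model with carry-over covariates, and SAP 4.2.2 has a first-period-baseline model.
- Pre-dose drug levels in periods following AZD8871 are listed (SAP 4.3.1.1).
- The final list of deviations is settled blind (SAP 2.2).

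So a reader who inferred that the plan has no guard against carry-over would go too far. But the safeguards are partial. The stability limit of 200 mL is twice the 100 mL target difference. First-period FEV1 is constant within a patient, so it cannot show which treatment came before. The drug-level listing covers the subset of 36 and has no efficacy rule attached. The blind review could revise the list, but items 58, 60 and 66 carry a plain No, not the +++ mark reserved for review, and item 67 covers only other deviations.

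A reader might also infer that the SAP drops a whole period for one home dose 61 minutes late. The ++ footnote does not fix that; what stands is that the unit is undefined. Nor are the smaller pair counts a forecast. They need the period reading, an assumed rate and independence. Lateness clustered within patients would leave more pairs intact, and the planned mixed model keeps patients with one missing period.

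Finally, item 44, "Patient did not fulfill fasting requirements on Day 1, 8, and 14 before IP administration and following dose administration", is also Yes++. It might look like the same misplacement, but item 47 independently excludes for lapses under Protocol 5.3, which holds the fasting rules. The documents do not show the coding to be wrong.

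**Conclusion.** The concern holds for items 66, 60 and 58: their coding departs from the SAP's own per-protocol definition and from the protocol's stated reason for the 42-day minimum. For item 55 it holds only as an ambiguity, with a cost ranging from nothing to the illustrative losses shown above.

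The bias from retained short wash-outs or mistimed readings cannot be sized, because the documents give neither their frequency nor the effect they would have. I also found no numerical spirometry window in the protocol or SAP text supplied.

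The consequence is limited. The per-protocol analysis is a sensitivity analysis in an exploratory study, and the full-set primary result does not change. The change is still worth making, because the analysis cannot serve its stated internal-validity purpose for these two deviations.

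**What to change.** Before unblinding, amend SAP Table 1 as follows:

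1. Split item 66. Code a period whose first dose falls less than 42 days after the previous period's last dose as Yes++ for the per-protocol set, at period level. Leave other visit-window deviations at No.
2. Code item 60, and item 58 for spirometry, as Yes++ at time-point level for Day 1 baseline and Day 15 trough readings outside their window, and state or cite that window. SAP 3.1 and 3.3.1 already use the remaining reading when one of two is missing, so a single excluded reading need not cost the period.
3. State under item 55 that an isolated mistimed home dose is not a period-level exclusion. Keep missed doses reviewable for the per-protocol set: the row's wording also catches doses never taken, and Table 1 has no compliance threshold, so simply narrowing the row could let such patients through.

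Leave item 44 unchanged.

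The cost is a few edited rows and, in the data, a few periods or readings leaving the per-protocol set. The full analysis set is untouched.
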